Surgical site infections (SSI) are the second most common cause of nosocomial infections accounting for 15% of all nosocomial infections among hospitalized patients and 38% of nosocomial infections in surgical patients. In obstetric patients, infectious morbidity (i.e. SSI, endometritis) occurs in 5-10% of cesarean sections, which is 5-fold higher than vaginal deliveries. Additionally, infectious morbidity is thought to be highest in those patients who have cesarean sections after undergoing labor.

Chlorhexidine, chemical antiseptic effective on gram positive and gram negative bacteria, reduces skin microflora/colonization but it is not clear if it decreases the risk of SSI.

Historically, chlorhexidine has been studied and used in orthopedic and cardiac implant surgeries. Research on the use of chlorhexidine for SSI prevention in cesarean sections is limited. This study intends to evaluate the effectiveness of use of both chlorhexidine gluconate (CHG) wipe and vaginal scrub with betadyne in reducing SSI in patients undergoing cesarean section that have previously been laboring. Patients will be randomized to one of two groups: wash with a pre-operative CHG cloth and chlorhexidine scrub prior to surgery (in addition to standard preoperative scrub) and standard preoperative scrub.

Primary and Secondary Study Endpoints

The primary outcome will be SSI and postpartum endometritis. Secondary outcomes include other maternal complications or interventions, neonatal ICU admissions, maternal length of stay or readmissions.

Subjects

800

Specify Other Setting of Human Research

Mount Sinai Hospital labor and delivery floor

Feasibility of Meeting Recruitment Goals

Researchers will have access to all patients scheduled for delivery at Mount Sinai Medical Center. About 1800 deliveries by cesarean section occur each year at Mount Sinai. Of these, approximately 800 are cesarean sections after failed labor. Assuming a primary outcome rate of 20% in the control arm, a sample size of 329 in each group would give 80% power to detect a 40% reduction in surgical site infection between the active group and control. We aim to recruit 400 patients per group (for a total of 800 patients) to account for patient drop out or non-compliance.

Due to the amount of deliveries and volume, we anticipate these recruitment goals to be feasible.

Facilities to Be Used for Conducting Research

Labor and Delivery floor at Mount Sinai Hospital

Inclusion Criteria

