Description of Procedures taken to lessen the probability of magnitude of risks

There is always the risk of loss of confidentiality; however, there are procedures in place to minimize this risk. To ensure confidentiality, the following system will be adhered to: When subjects are enrolled in this study, they will be assigned a unique identification code. Corresponding medical record numbers for each code (key code) will be stored in a password locked document on the maternal-fetal medicine (MFM) server that can be accessed only by members of the research team. At the conclusion of the data extraction, the outcome variable will be assessed and the key codes to the medical record numbers will no longer be necessary and that information will be permanently erased from the key code file. Electronic data with identifiers will be encrypted according to Data Security Standards.

Provisions for Research Related Harm / Injury

The patients will receive standard obstetric care and have access to the obstetric staff (physicians, nursing) as well as all of the resources on the labor floor including the use of the operating room, blood bank, and continuous fetal

monitoring. Any potential adverse events are inherent to the operative delivery itself and regardless of the study. Any complications that occur during cesarean section will be managed by the obstetricians and anesthesiologists. As standard of care, a physician is present during a cesarean section and is experienced in managing complications. The patient is billed as per standard scheduled cesarean section regardless of complications due to the surgery.

Expected Direct Benefit to Subjects

Direct benefit to subject is unknown. However, the potential benefit is that we may find a reduction in infectious morbidity related to cesarean section.

Benefit to Society

Direct benefit to society is unknown. However, the potential benefit is that we may find a reduction in infectious morbidity related to the cesarean section surgery which may reduce subsequent healthcare costs due to decreased readmissions for surgical site infections.

Provisions to Protect the Privacy Interests of Subjects ***

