The patients will be approached upon admission to the labor and delivery floor by a physician. Their participation will not require any additional examinations. All research-related discussions will be held in a private location. Any questions will be answered and fully discussed to maximize patient comfort. If they choose to participate they will be randomized and receive care within the accepted standards. If a patient must be called to find out how the wound is healing, the research team members placing the call will not leave a message or speak to anyone except the patient herself. When called, she will be asked if she can discuss the research study at that time, ensuring patient privacy and comfort.

Economic Impact on Subjects

There are no foreseeable costs that subjects may incur through participation in the research.

Data for Assessing Potential Risks to Pregnant Women and Fetuses

The risks to pregnant women and fetuses are inherent to the cesarean section process itself outside of the study. The only difference in care is use of chlorhexidine gluconate in one arm of the study. This may result in a decreased rate of infectious morbidity.

If used as instructed, the only potential unforeseeable risk is an allergic reaction to the chlorhexidine gluconate. Allergic reaction could include itching or hives, swelling in the face or hands, swelling or tingling in the mouth or throat, chest tightness, and/or trouble breathing.

Description of the study design

This is a prospective randomized trial.

The study will be offered to women who are admitted to Mount Sinai Medical Center to undergo labor. The eligible women will be randomized to use of a 2% chlorhexidine gluconate (CHG) cloth and vaginal scrub (in addition to standard preoperative scrub) or standard preoperative scrub alone. Participants will not be blinded to the arm in which they have been assigned. This study intends to show that the use of chlorhexidine cloth and vaginal scrub prior to cesarean section will reduce the rate of SSI in women who have previously been laboring.

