Researchers will have access to all patients scheduled for delivery at Mount Sinai Medical Center. About 1800 deliveries by cesarean section occur each year at Mount Sinai. Of these, approximately 800 are cesarean sections after failed labor. Assuming a primary outcome rate of 20% in the control arm, a sample size of 329 in each group would give 80% power to detect a 40% reduction in surgical site infection between the active group and control. We aim to recruit 400 patients per group (for a total of 800 patients) to account for patient drop out or non-compliance.

Description of Procedures Being Performed

This study intends to evaluate the effectiveness of a chlorhexidine gluconate (CHG) cloth and vaginal scrub in reducing SSI in patients undergoing cesarean section who have previously been laboring. Patients will be randomized to one of two groups: administration of a 2% CHG cloth and vaginal scrub (in addition to standard preoperative care) prior to cesarean delivery or standard preoperative care.

Description of the Source Records that Will Be Used to Collect Data about Subjects

All data will be extracted from electronic medical records (EMR) and phone calls made to subjects if they do not present for their postpartum visit.

Description of Data that Will Be Collected Including Long-Term Follow-Up

Data that will be collected from the EMR include maternal demographics (age, race, BMI, parity) as well as outcomes including surgical site infection and postpartum endometritis. In addition data will be collected regarding other outcomes including maternal complications or interventions, neonatal ICU admissions, maternal length of stay or readmissions. This data collection will start from time of enrollment to 6 weeks postpartum.

Where and When Consent Will Be Obtained

Consent will be obtained upon admission to the labor and delivery floor at Mount Sinai Hospital.

Waiting Period for Obtaining Consent

The patient can be approached and consented starting from admission to labor and delivery and can still be consented to participate in the study at a later time in labor if not already delivered by cesarean section.

Description of Health Information That Will Be Viewed, Recorded, or Generated

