Health information collected will include maternal age, parity, gestational age, medical problems, number of previous cesarean sections, indication for cesarean section, time from incision to delivery, type of anesthetic, type and use of prophylactic antibiotics and type of wound closure. Maternal outcomes including estimated blood loss (EBL) will be reviewed. Charts will be reviewed through the 6 week postpartum visit in order to determine how well the skin at the incision site is healing. If patients do not visit Mount Sinai Medical Center for their 2 week wound check, they will be called and asked the following questions: Were you treated for wound infection? Did you experience wound separation or any other wound complications?

Description of Non-Health Information That Will Be Viewed or Recorded

Data collected will include demographic variables such as age, parity, body mass index (BMI) and race.

How PHI Will Be Protected from Improper Use or Disclosure

No specimens will be sent out or received in this trial.

All data is de-identified; patients are followed by subject number. Identifiable patient information (consent forms & consent documentation) are kept separately from any data collected. All consent documentation is stored in a locked cabinet at [REDACTED]. Identifiable enrollment statistics are kept in a password-protected computer (Excel) spreadsheet that is only accessible by members of the research team on a departmental J Drive.

When and How PHI Will Be Destroyed

The key code and data points will be destroyed 7 years after data analysis is complete.

Description of PHI that Will Be Shared

PHI that will be shared will include maternal demographics and maternal outcomes as previously described. Maternal demographics and information collected will include age, parity, BMI, race, gestational age, and number of previous cesarean sections. Additional information will be recorded and shared including time from incision to delivery, type of anesthetic, antibiotic use, type of wound closure, and EBL. Charts will be reviewed through the 6 week postpartum visit in order to determine how well the skin at the incision site is healing.

Justification for Sharing PHI

The PHI will be shared for means of data analysis by members of the research team and statisticians.

With Whom Directly PHI Will Be Shared

The PHI will be shared with members of the research team

Location Where Data Will Be Stored

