All research data will be stored in a password-protected database maintained on a secure network drive on the hospital server.

Duration Data Will Be Stored

The key code and data points will be destroyed 7 years after analysis is complete.

Steps That Will Be Taken to Secure the Data During Storage, Use, and Transmission

To minimize risk of loss of confidentiality, study subjects will be assigned a unique identification code. The unique ID code will be linked to the subject's medical record number. The linking key code will be encrypted and stored separately on a secure excel spreadsheet accessible only by the PI and research staff. All research data will be stored in a password-protected database maintained on a secure network drive on the hospital server.

Steps That Will Be Taken to Secure the Data During Storage, Use, and Transmission

To minimize risk of loss of confidentiality, study subjects will be assigned a unique identification code. The unique ID code will be linked to the subject's medical record number. The linking key code will be encrypted and stored separately on a secure excel spreadsheet accessible only by the PI and research staff. All research data will be stored in a password-protected database maintained on a secure network drive on the hospital server.

Data Analysis Plan Including Any Statistical Procedures

Data will be analyzed on an intention to treat basis. Statistical analysis will be performed by SAS using X 2 test or Fisher exact test (categorical variables) and student t test or Mann-Whitney U test (continuous variables). Statistical significance will be set at $p<0.05$.

Study Fund Account (or alternate departmental / fund account, if study is not yet established)
[REDACTED]

Generic Name

4% chlorhexidine gluconate

Brand Name

BD E-Z Scrub 107 Surgical Scrub Brush/Sponge 4% Chlorhexidine-Gluconate

IND Number

[REDACTED]

Name of IND Holder

[name]

Drug / Biologic Description (Manufacturer/Generic Name/Form/Strength)

Drug: BD E-Z Scrub 107 Surgical Scrub Brush/Sponge 4% Chlorhexidine-Gluconate

Biologic Description: Antiseptic

Manufacturer: Becton, Dickinson and Company

Generic Name: 4% chlorhexidine gluconate

Form: Scrub Brush/Sponge

Strength: 4% chlorhexidine gluconate w/v

Effective Date: 3/11/2022

End Date: 3/10/2023

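### Nothing in the plan keeps whoever abstracts the chart or makes the follow-up call unaware of the arm, and the infection outcome has no written criteria, so classification can differ by arm

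*Combined protocol and SAP*

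**What the plan says.** The protocol carries its own analysis section, and all references are to that one document.

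- **Masking.** *Description of the study design*: "Participants will not be blinded to the arm in which they have been assigned". This covers participants only. No section mentions masking of the chart abstractor, the caller or anyone who classifies outcomes.
- **Primary outcome.** *Primary and Secondary Study Endpoints*: "The primary outcome will be SSI and postpartum endometritis". No section gives diagnostic criteria for either component.
- **Source.** The section on source records states: "All data will be extracted from electronic medical records (EMR) and phone calls made to subjects", the calls being for women who do not attend their postpartum visit. *Description of Health Information That Will Be Viewed, Recorded, or Generated* has charts reviewed to the 6-week visit to judge wound healing. A woman who misses the 2-week wound check is asked: "Were you treated for wound infection? Did you experience wound separation or any other wound complications". Endometritis is not asked about.
- **Who does it.** *Provisions to Protect the Privacy Interests of Subjects* refers to "the research team members placing the call will not leave a message or speak to anyone except the patient herself". The abstractor is not named.
- **Coding.** *How PHI Will Be Protected from Improper Use or Disclosure*: "All data is de-identified; patients are followed by subject number". *Steps That Will Be Taken to Secure the Data During Storage, Use, and Transmission*: "The unique ID code will be linked to the subject's medical record number". The risk-reduction section keeps the key in a file "that can be accessed only by members of the research team".
- **Analysis.** *Data Analysis Plan*: intention to treat, chi-square or Fisher exact test, significance at p<0.05.

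**The concern.** Whether a red wound edge, a partial separation or a postpartum fever counts as an event is a judgement. With no written criteria, that judgement falls to whoever reads the chart or turns a phone answer into a yes or no. The design section states that the study sets out to show a reduction, so the team's expectation has a direction. If the person judging knows the arm, borderline cases can be resolved differently in the two groups.

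That is differential misclassification of the primary outcome. Intention to treat protects the comparison of groups as randomised, and the chi-square test allows for chance. Neither deals with events counted differently by arm. At stake is whether a significant result can be read as an effect of the preparation.

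**Working it through.** **Inputs from the protocol.** Control rate 20%, relative reduction 40% (so 12% in the active arm), power 80%, 329 per arm required and 400 recruited (*Feasibility of Meeting Recruitment Goals*; *Description of the study design*). Significance level 0.05, sidedness not stated (*Data Analysis Plan*). Background infectious morbidity 5-10% of cesarean sections (*Background*).

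**Assumed input.** r is the relative reduction in recorded events in the chlorhexidine arm that is due to classification alone. The documents give no value, so a range is shown.

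**Step 1: reproduce the plan's figure.** Two-sided 0.05, pooled variance, no continuity correction:

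n = [1.960 × √(2 × 0.16 × 0.84) + 0.8416 × √(0.20 × 0.80 + 0.12 × 0.88)]² / 0.08² = [1.960 × 0.5185 + 0.8416 × 0.5154]² / 0.0064 = 1.4499² / 0.0064 = 328.5, so 329.

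This matches. A one-sided test would need 259, so two-sided is taken as intended. The sample size is not at fault on this point.

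**Step 2: chance of a significant result favouring chlorhexidine when there is no true effect.** Let pC be the control rate, pT = pC(1 − r) the recorded active rate, and p̄ their mean.

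P = Φ[(pC − pT − 1.960 × s0) / s1], with s0 = √(2p̄(1 − p̄)/n) and s1 = √([pC(1 − pC) + pT(1 − pT)]/n).

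Example, n = 400 and r = 10%: pC = 0.20, pT = 0.18, p̄ = 0.19, s0 = 0.02774, s1 = 0.02773. Then (0.02 − 1.960 × 0.02774)/0.02773 = −1.239, and Φ(−1.239) = 10.8%.

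| True rate, both arms | n per arm | r = 0 | r = 10% | r = 15% | r = 20% |
|---|---|---|---|---|---|
| 20% | 400 | 2.5% | 10.8% | 19.3% | 31.3% |
| 20% | 329 | 2.5% | 9.6% | 16.6% | 26.6% |
| 10% | 400 | 2.5% | 7.0% | 11.0% | 16.6% |

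The starting point is 2.5%, not 5%, because only one direction of a two-sided 5% test is a false benefit.

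**Step 3: the same in counts.** At 400 per arm and 20%, 400 × 0.20 = 80 events are expected in each arm. The three shifts are 8, 12 and 16 of those 80.

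**Step 4: the other direction.** If recorded active-arm events were raised by 10% instead (pT = 0.22, p̄ = 0.21, s0 and s1 both about 0.0288), the chance of a significant false harm would be Φ[(0.02 − 1.960 × 0.0288)/0.0288] = 10.3%. The arithmetic does not favour either direction.

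**The case against.** The strongest case against is that the outcome is less exposed than it looks. Most events will be diagnoses charted in routine care, since participation adds no examinations. The phone call is only a fallback, covers wound events only, and already uses set questions that do not mention the arm. The first asks about a fact, namely treatment for infection. This stands, and it limits the phone route. It does not close the chart route: with no criteria, someone still decides what in the record counts as an event, and nothing keeps that person unaware of the arm.

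A second objection is that masking the abstractor does not touch a participant's own report, or a diagnosis charted by a clinician who knows the arm. That also stands. It makes the protection partial, not worthless.

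Third, data are held under a coded ID, which might be read as masking. It is not. The code protects confidentiality, the key is open to the research team, and the abstractor must open the woman's record in any case. The coding passages say nothing about allocation either way.

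Two stronger readings are tempting and unsupported. A reader might infer that the staff who enrolled or randomised a woman will also classify her outcome. The protocol does not say so; it only fails to prevent it. A reader might also infer that the result will be biased towards chlorhexidine. The documents give neither a direction nor a size. The 20% scenario needs 16 of 80 events lost to classification alone, half of the 40% effect the trial is designed to detect, and nothing in the protocol suggests a shift that large.

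**Conclusion.** The point holds as a gap in outcome ascertainment. Participants are unmasked, nothing masks the abstractor or caller, and the primary outcome has no written criteria, so the plan as written permits classification with knowledge of the arm.

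The size is unknown. With no true effect and a 20% control rate, a 10% relative under-count in the chlorhexidine arm would raise the chance of a significant false benefit from 2.5% to 10.8% at 400 per arm, or to 9.6% at 329. With a true rate of 10% it would be 7.0% at 400 per arm. These figures rest on an assumed shift, a two-sided pooled test and the normal approximation. They show sensitivity and do not predict what will happen.

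A reader might infer that leaving participants unblinded is itself the fault. It is not the point here: a wash and scrub added to standard preparation are hard to conceal from the woman, and the remedy does not require it. This is a cheap improvement to the plan, and neither the design nor the sample size needs to change.

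**What to change.** 1. Assign chart abstraction and follow-up calls to an existing team member who did not enrol, randomise or prepare that woman.
2. Keep the allocation list in a file separate from the outcome form and closed to that person.
3. Keep the two existing phone questions as the fixed script, with no mention of the arm. Reconcile the call trigger, which is a missed postpartum visit in one section and a missed 2-week wound check in another.
4. Write down criteria for surgical site infection and endometritis, including how a phone answer is counted, and lock each classification before allocation is merged.
5. Record, and report by arm, how often the abstractor became aware of the allocation and how many outcomes came from phone report.

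Do not exclude women whose chart revealed the arm, even as a sensitivity analysis. A note of chlorhexidine preparation would arise mainly in the active arm, so exclusion would be lopsided and would depart from intention to treat. For illustration, assume 20% infected in both arms, no control exclusions, and notes that reveal the arm for 60% of infected and 40% of uninfected chlorhexidine women. The retained active rate is (0.20 × 0.40)/(0.20 × 0.40 + 0.80 × 0.60) = 0.08/0.56 = 14.3% against 20%, a false benefit created by the check.

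**Cost.** Some reallocation of tasks, a short criteria document and an extra item or two on the form. No added patients or visits, and no change in care. It assumes the team is large enough to divide the work. *How Participants will be screened* lists several roles but no numbers. Masking will be partial: chart notes may reveal the preparation, and neither participants' own reports nor diagnoses charted by clinicians who know the arm are masked.

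### The scripted follow-up call asks only about the wound, so endometritis treated outside the EMR after discharge can be missed in women who do not return; the effect is probably small and the remedy cheap

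*Combined protocol and SAP*

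**What the plan says.** All references are to the combined protocol and SAP.

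- **Outcome.** Primary and Secondary Study Endpoints: "The primary outcome will be SSI and postpartum endometritis". Readmissions are a secondary outcome.
- **Window.** Description of Data that Will Be Collected Including Long-Term Follow-Up lists "outcomes including surgical site infection and postpartum endometritis" among the EMR items, and adds: "This data collection will start from time of enrollment to 6 weeks postpartum".
- **Sources.** Description of the Source Records: "All data will be extracted from electronic medical records (EMR) and phone calls made to subjects if they do not present for their postpartum visit". The protocol describes no request for outside records and no contact with other providers.
- **Call script and first trigger.** Description of Health Information That Will Be Viewed, Recorded, or Generated sets the call for women who miss the 2-week wound check and gives its questions: "Were you treated for wound infection? Did you experience wound separation or any other wound complications". The same paragraph has charts reviewed through a postpartum visit at 6 weeks.
- **Purpose of the call.** Provisions to Protect the Privacy Interests of Subjects mentions the call in passing: "If a patient must be called to find out how the wound is healing". Staff may leave no message and may speak only to the woman herself.
- **Second trigger.** The Source Records sentence ties the call to a missed postpartum visit, with no week stated.
- **Blinding.** Description of the study design: "Participants will not be blinded to the arm in which they have been assigned".
- **Sample size.** The same section gives 329 per group for 80% power, then: "We aim to recruit 400 patients per group (for a total of 800 patients) to account for patient drop out or non-compliance".

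**The concern.** The two components of the primary outcome are ascertained to different standards in women who do not come back. A wound infection treated elsewhere is asked about. Endometritis treated elsewhere is not, because the catch-all in the second question is limited to wound complications. A woman might volunteer the information, but the script does not ask for it.

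The trigger adds a second, conditional gap. If only a missed 2-week check prompts a call, a woman who attends at 2 weeks and misses the 6-week visit is never contacted, and a call made near week 2 cannot cover the remaining weeks.

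At stake is under-counting of the primary outcome. If the missed cases are analyzed as event-free, both observed rates fall and the absolute difference shrinks. The relative reduction is unchanged only if the same share of events is lost in each arm. The lost events all belong to one component, so if the intervention acts differently on endometritis and on SSI, the composite relative effect could also shift, in a direction the documents do not let us predict. An event never asked about may be hard to recover later, and the Data Analysis Plan has no step that addresses it.

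**Working it through.** **1. Reproduce the plan's figure.** Inputs from the protocol: control rate 20%, 40% reduction (so 12%), 80% power, significance at 0.05 (sidedness not stated; two-sided assumed). The pooled-variance two-proportion formula without continuity correction gives 329 per group, matching the protocol. Power is 80.1% at 329 and 87.1% at 400. The 400-per-arm figure assumes no drop-out.

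**2. Wording gap.** None of the shares below is in the documents; all are assumptions, with equal loss in both arms and missed cases analyzed as event-free.

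L = e × d × m × o, where
- e = endometritis-only events as a share of primary events: 0.30 to 0.50, mid 0.40
- d = share of these arising after discharge: 0.25 to 0.75, mid 0.50
- m = women not returning: 0.10 to 0.30, mid 0.20
- o = share of their cases treated outside the EMR: 0.30 to 1.00, mid 0.50

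Both rates are multiplied by (1 − L). Expected events at 400 per arm are 400 × 0.20 = 80 control and 400 × 0.12 = 48 active.

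| Case | L | Events lost, control / active | Difference (points) | Power at 400 |
|---|---|---|---|---|
| None lost | 0 | 0 / 0 | 8.00 | 87.1% |
| Low: 0.30 × 0.25 × 0.10 × 0.30 | 0.00225 | 0.2 / 0.1 | 7.98 | 87.0% |
| Mid: 0.40 × 0.50 × 0.20 × 0.50 | 0.020 | 1.6 / 1.0 | 7.84 | 86.3% |
| High: 0.50 × 0.75 × 0.30 × 1.00 | 0.1125 | 9.0 / 5.4 | 7.10 | 82.2% |

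Moving one share at a time from the mid-case: e gives 0.015 to 0.025, d gives 0.010 to 0.030, m gives 0.010 to 0.030, and o gives 0.012 to 0.040. The one-at-a-time range is therefore 1.0% to 4.0% of primary events, with power from 86.7% to 85.5%.

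**3. Trigger gap, only if the 2-week check is the sole trigger.** Again all shares are assumed.

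L = a × s × g × o, where
- a = primary events arising after the 2-week check: 0.05 to 0.30, mid 0.15
- s = women seen at 2 weeks: 0.70 to 0.90, mid 0.80
- g = of those seen, the share who miss the 6-week visit: 0.10 to 0.40, mid 0.20
- o = as above

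The factor s is needed because g applies only to women seen at 2 weeks, while L is a share of all primary events.

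Mid: 0.15 × 0.80 × 0.20 × 0.50 = 0.012, or 1.2% of events. That is 80 × 0.012 = 1.0 control and 48 × 0.012 = 0.6 active events, with power 86.7%. With a, g and o at maximum, L = 0.30 × 0.40 × 1.00 × s = 0.12 × s, or 8.4% to 10.8%.

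Late endometritis treated elsewhere can fall into both gaps, so the losses in steps 2 and 3 overlap and should not be added.

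**4. Cost of asking unblinded women.** Assumed example: 20% of women are called, and 3% of event-free control women against 1% of event-free active women wrongly report endometritis.
- Control: 0.20 + 0.80 × 0.20 × 0.03 = 0.2048, which adds 1.9 events.
- Active: 0.12 + 0.88 × 0.20 × 0.01 = 0.1218, which adds 0.7 events.
- Difference: 8.3 points instead of 8.0.

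**The case against.** **The effect is small and assumed.** This stands. The mid-case is fewer than three events across 800 women, and every share is assumed. The loss also requires that the missed cases be analyzed as event-free. The Data Analysis Plan states no such rule, and women handled as drop-outs are what the move from 329 to 400 is meant to cover.

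**The trigger conflict may not be real.** This largely stands. The only postpartum visit with a week attached is the 6-week one. If the Source Records sentence means that visit, or if both triggers apply, a woman who misses it is called. What remains is that the text does not say so.

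**Asking may replace missed events with false ones.** This stands in part. In step 4 the false reports total 1.9 + 0.7 = 2.6 events, as many as the 1.6 + 1.0 = 2.6 true events lost in the mid-case, and they widen the difference rather than shrink it. Excluding self-reports not confirmed in a record is only a partial safeguard: without outside records, that analysis is close to the current plan.

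**The contrast between components depends on contact.** This also stands. A wound infection is found only if the woman is reached and the event precedes the call. Added questions will therefore recover fewer events than step 2 shows as lost.

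**Stronger readings that the documents do not support.** A reader might infer that endometritis goes uncollected. It is named among the EMR outcomes, so cases in the delivery stay or charted at a later visit are captured. A reader might infer a biased treatment effect. The documents give no evidence that return rates differ by arm. A reader might apply these losses at 329 per arm as a power shortfall. The protocol sets 329 for 80% power and 400 to allow for drop-out, so 400 is the planned base here.

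**Conclusion.** The point holds as a modest gap in outcome ascertainment. Followed as written, the call does not ask about one named component of the primary outcome, and the gap is limited to post-discharge endometritis treated outside the EMR in women who do not return. On the assumed shares, roughly 2% of primary events are lost; the figure near 11% needs all four shares at their maximum together. The power cost in the mid-case is under one percentage point. The trigger gap exists only under the narrower reading and is about 1.2% in the mid-case.

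The change is worth making because it improves measurement of the primary outcome through a call already planned. It is a cheap improvement and does not put the trial's conclusion in doubt.

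**What to change.** 1. In both arms, with identical wording, add to the existing call: whether the woman was treated for an infection of the uterus; whether she was readmitted or treated for an infection anywhere else; and where and when. The readmission question also serves a secondary outcome.
2. Reconcile the Source Records and Health Information sections. State which visit is meant, and have a call cover the end of the 6-week window for any woman not seen at that point.
3. Count reported endometritis by one prespecified rule applied alike in both arms.
4. Present the primary result with and without self-reported cases not confirmed in a record, as bounds, noting that without outside records the analysis excluding them is close to the current plan.
5. Report by arm the number of women neither seen nor reached.

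**Cost.** A few added questions, some extra short calls and an amendment. Requesting outside records would strengthen item 4, but it adds a source beyond the two the protocol names and may need further authorization, so it is optional. The main downside is that self-report by unblinded women may differ by arm; items 3 and 4 make that visible but do not remove it.
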